4. AMENDMENTS AND UPDATES

Significant updates have been made to the data source and analytical approach compared to the original OCEANMIST protocol submission. Below, we provide a high-level overview of the key differences with additional details described in Sections 5-8 and Section 12 below.

Data Source Updates

• In this study, data for encorafenib plus binimetinib patients will be pooled from the phase 3 COLUMBUS trial and the Flatiron Health real-world database to maximize sample size. In contrast, the original study design, only used encorafenib plus binimetinib data from Flatiron Health. This pooling is justified based on the empirical consistency in OS outcomes across COLUMBUS and Flatiron Health after harmonizing key patient selection criteria, adjusting for differences in baseline characteristics, and imputing missing data on baseline characteristics (HR = 1.03, 95% CI: 0.53, 1.54; p=0.90), described in study C4221035.

Analytical Approach Updates

- To ensure identification of patient populations in Flatiron that are comparable to patients in the COLUMBUS trial, key patient selection criteria related to age, ECOG performance score, history of brain metastasis and prior use of immunotherapy and targeted therapies from the COLUMBUS trial will be applied to all treatment groups in Flatiron Health.
- To ensure that representation of each targeted therapy from the real-world data was as comprehensive as possible and that patients were followed from treatment initiation consistent with the COLUMBUS trial, patients included in each treatment cohort will be required to have index dates (i.e., treatment initiation dates) that were on or after the dates of FDA approval of that targeted therapy in metastatic melanoma (specifically, 09 January 2014 for DAB+TRAM, 10 November 2015 for VEM+COBI and 27 June 2018 for ENCO+BINI). This is in contrast to the original approach, which defined the follow-up period for all cohorts as beginning from 20 November 2015. This could have led to the exclusion of some patients initiating DAB+TRAM before approval, and could potentially inadvertently include off-label usage of ENCO+BINI.

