8.2.1.1. COLUMBUS trial

Key inclusion criteria in the COLUMBUS trial were:

- Histologically confirmed diagnosis of locally advanced, unresectable, or metastatic cutaneous melanoma or unknown primary melanoma
- American Joint Committee on Cancer (AJCC) disease stage of IIIB, IIIC, IVM1a, IVM1b, or IVM1c at trial enrolment
- Presence of BRAF V600E or V600K mutation in tumor tissue prior to enrollment
- At least 18 years of age at randomization
- Eastern Cooperative Oncology Group (ECOG) status of 0 or 1 at randomization
- Treatment naive or had progressed on or after previous first-line (1L) immunotherapy at randomization with no prior BRAF- or MEK-inhibitor therapy in the adjuvant setting

Patients from the COLUMBUS trial included in this analysis will be those patients:

Randomized to ENCO+BINI arm of the trial to receive 450mg once daily encorafenib
and 45mg twice daily binimetinib combination therapy

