- VEM+COBI treatment group: At least 1 order or administration of VEM+COBI treatment after the diagnosis of metastatic melanoma and after 10 November 2015 (FDA approval date for VEM+COBI for use in patients with metastatic melanoma).

The index date in each treatment group will be the date of treatment initiation.

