8.3. Variables

Table 1 provides a summary of exposure, outcome, and patient baseline characteristics that will be evaluated within the study.

Table 1. Key exposures, outcomes, and patient baseline characteristics

Variable	Role	Data source(s)	Operational definition/categories
Treatment group (ENCO+BINI, DAB+TRAM, VEM+COBI)	Exposure	COLUMBUS trial data; Flatiron EHR	Indicates whether patients initiated ENCO+BINI, DAB+TRAM or VEM+COBI treatment
os	Primary Outcome	COLUMBUS trial data, Flatiron	In the COLUMBUS trial data, defined as the time from the date of randomization to the date of death due to any cause; if death is not observed, patients will be censored at the date of last contact or the data analysis cut-off date (e.g., 15 September 2020), whichever occurs first
	Timaly outcome		In Flatiron EHR, will be defined as the time from the index date to the date of death; patients without a date of death will be censored at their last known activity date (e.g., the last clinical note date) or the end of the follow-up period, whichever occurs first
	COLUMBUS	In the COLUMBUS trial data, defined as the time from the date of randomization to the date of the first documented disease progression or death due to any cause, whichever occurred first; if a patient did not have an event at the analysis cut-off date, PFS will be censored at the date of the last adequate tumour assessment	
PFS	Exploratory Outcome	trial data, Flatiron her	In Flatiron EHR, will be defined as the time from the index date to either the date of first disease progression event or death in the absence of progression; patients without disease progression or death will be censored at the last date the patient could have been assessed for progression (e.g., the last clinical note date) or the data analysis cut-off date (e.g., 30 September 2021), whichever occurs first
Age at baseline (years)	Baseline Characteristic / Potential Confounder	COLUMBUS trial data Flatiron EHR	Patient age; defined at the time of study randomization for COLUMBUS trial data and at the time of treatment initiation for Flatiron EHR
Sex	Baseline Characteristic / Potential Confounder	COLUMBUS trial data; Flatiron EHR	Male, Female, Intersex, or Unknown/Missing

Race	Baseline Characteristic / Potential Confounder	COLUMBUS trial data; Flatiron EHR	Asian, Black, White, Other/Multi-Race, or Unknown/Missing

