5.1 EFFICACY/EFFECTIVENESS ENDPOINT(S)

Table 2 provides a summary of efficacy/effectiveness endpoints that will be evaluated within the study.

Table 2 Clinical outcomes of interest for efficacy/effectiveness

Variable Operational definition					
OS	In the COLUMBUS trial data, defined as the time from the date of randomization to the date of death due to any cause; if death is not observed, patients will be censored at the date of last contact or the data analysis cut-off date (e.g., 15 September 2020), whichever occurs first				
OS	In Flatiron EHR, will be defined as the time from the index date to the date of death; patients without a date of death will be censored at their last known activity date (e.g., the last clinical note date) or the end of the follow-up period, whichever occurs first				
	In the COLUMBUS trial data, defined as the time from the date of randomization to the date of the first documented disease progression or death due to any cause, whichever occurred first; if a patient did not have an event at the analysis cut-off date, PFS will be censored at the date of the last adequate tumour assessment				
PFS	In Flatiron EHR, will be defined as the time from the index date to either the date of first disease progression event or death in the absence of progression; patients without disease progression or death will be censored at the last date the patient could have been assessed for progression (e.g., the last clinical note date) or the data analysis cut-off date (e.g., 30 September 2021), whichever occurs first				

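### The pooled ENCO+BINI group mixes two time zeros: COLUMBUS patients are timed from randomization, all Flatiron patients from treatment initiation

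*Protocol*

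**What the plan says.** Protocol Section 8.3, Table 1 defines OS separately by data source. For the trial: "In the COLUMBUS trial data, defined as the time from the date of randomization to the date of death due to any cause". For the real-world data, SAP Section 5.1, Table 2 reads: "In Flatiron EHR, will be defined as the time from the index date to the date of death". Each document carries both definitions. Exploratory PFS has the same split: for COLUMBUS, "defined as the time from the date of randomization to the date of the first documented disease progression or death due to any cause"; for Flatiron, "In Flatiron EHR, will be defined as the time from the index date to either the date of first disease progression event or death".

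The last sentence of Protocol Section 8.2.1.2, repeated in SAP Section 4.1, is "The index date in each treatment group will be the date of treatment initiation". ENCO+BINI is pooled over COLUMBUS and Flatiron, while DAB+TRAM and VEM+COBI are Flatiron only (SAP Section 2.1).

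Exposure is defined by starting treatment: "Indicates whether patients initiated ENCO+BINI, DAB+TRAM or VEM+COBI treatment" (Protocol Table 1). COLUMBUS patients, however, are selected by allocation: "Randomized to ENCO+BINI arm of the trial to receive 450mg once daily encorafenib" (Protocol Section 8.2.1.1).

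**The concern.** In a comparison across data sources, follow-up should start at the same event in every group. Here the start depends on the source, and source is tied to treatment. Part of ENCO+BINI starts at randomization. The rest of ENCO+BINI and all of both comparators start at treatment initiation.

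For a COLUMBUS patient dosed after randomization, the days in between are added to OS and PFS. That patient is known to have survived to the first dose, so those days contain no death. No baseline covariate and no imputed value changes when the clock starts, so the adjusted Cox model does not remove the difference. The two optional sensitivity analyses in SAP Section 7.1 (further covariates, and calendar time of initiation) do not address it, and Protocol Section 8.9 does not list it as a limitation. At stake is a small source-specific artefact in the primary OS hazard ratio.

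**Working it through.** **What the documents supply.** They give the time-zero rules above and 192 patients randomized to ENCO+BINI in COLUMBUS Part 1 (Protocol Section 8.4). They do not give the gap from randomization to first dose, the number never treated, the COLUMBUS share of the pooled group, or any expected event count. There is no plan figure to reproduce, so the size below is an illustration under stated assumptions.

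**One patient.** Two patients start ENCO+BINI on day 0 and die on day 300. In Flatiron, with initiation dated at first dose, OS is 300 days. In COLUMBUS, with randomization 7 days before first dose, OS is 307 days.

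**Effect on the hazard ratio.** Assumptions: exponential survival, true HR 1, censoring 60 months after treatment start, gap g, and a COLUMBUS share s of the ENCO+BINI group. Approximation:

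HR multiplier = s / (1 + g / F) + (1 − s), where F = (1 − e^(−60λ)) / λ is mean follow-up in months and λ = ln 2 / median.

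Worked case, median 24 months, s = 0.8, g = 14 days:
- λ = 0.6931 / 24 = 0.02888 per month
- F = (1 − 0.1768) / 0.02888 = 28.5 months
- g = 14 / 30.4375 = 0.460 months, so g / F = 0.0161
- Multiplier = 0.8 / 1.0161 + 0.2 = 0.987

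Cox models fitted to simulated data (400,000 patients per group) agree with this. The outer columns are the extremes of the assumed ranges:

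| Gap | Median 12 mo, s = 1.0 | Median 24 mo, s = 0.8 | Median 36 mo, s = 0.6 |
|---|---|---|---|
| 7 days | 0.987 | 0.994 | 0.996 |
| 14 days | 0.973 | 0.987 | 0.992 |
| 28 days | 0.947 | 0.975 | 0.985 |

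A separate simulation with s = 0.75, a 24-month median and different censoring gave 0.992 for 7 days and 0.984 for 14 days. Appendix Table 3 uses ENCO+BINI as the reference, so the reciprocals apply there: 1/0.996 = 1.004 to 1/0.947 = 1.056 over the whole table.

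**Scale against sampling error.** With assumed deaths of 100 and 200, SE(log HR) = √(1/100 + 1/200) = 0.122, and the 95% CI factor is e^(1.96 × 0.122) = 1.27. With 130 and 300 deaths, the SE is 0.105 and the factor 1.23. The artefact is well inside either.

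**What could offset it.** The table only adds event-free days. Randomization-based OS also counts deaths before first dose. In simple rate terms the gain cancels if the number of such deaths equals n × g × λ, the deaths expected in the gap at the usual hazard. With n = 192 and a 24-month median:
- 7 days: 192 × 0.230 × 0.02888 = 1.3 deaths
- 14 days: 192 × 0.460 × 0.02888 = 2.6 deaths

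A handful of deaths before dosing would therefore be enough to remove or reverse the gain.

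**The case against.** The strongest defence is that the split is open and deliberate. Randomization is the COLUMBUS anchor throughout: eligibility age, ECOG, the age covariate, OS and PFS. The index-date sentence closes the Flatiron subsection, directly after the Flatiron cohort rules, so it may be meant for Flatiron alone. Section 8.9 of the Protocol calls the analysis analogous to intent-to-treat, for which randomization is the usual start.

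Part of this stands. A reader might infer that the plan plainly breaks its own index-date rule. The placement of the sentence does not support that, and the fair description is an unreconciled inconsistency. The amendment sections of both documents state as the aim that "patients were followed from treatment initiation consistent with the COLUMBUS trial". This shows the intention, but it sits in a rationale for the approval-date rule and cannot carry the point. The defence does not dispose of the mismatch, because on either reading the endpoint tables start the clock at different events. The intent-to-treat remark concerns adherence and later treatments, and no comparator patient was randomized.

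A reader might also infer that the bias always favours ENCO+BINI, or applies to the whole group. The documents support neither:
- The Flatiron part of ENCO+BINI is timed like the comparators.
- Deaths before dosing count under the randomization rule and have no Flatiron counterpart.
- Patients never treated, or dosed on the day of randomization, gain no such time.
- Flatiron cohorts qualify by either an order or an administration. If initiation is dated from an order, comparator patients carry some pre-dose time too.

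**Conclusion.** The point holds in limited form. Within ENCO+BINI, and only there, OS and PFS start at two different events, and no planned analysis would show what difference this makes. For treated COLUMBUS patients the mismatch lengthens follow-up by the gap. The ENCO+BINI hazard ratio would be multiplied by about 0.99 for a 7-day gap and 0.97 to 0.99 for 14 days. This assumes exponential survival, medians of 12 to 36 months, a COLUMBUS share of 60% to 100%, and no deaths before dosing. The net direction cannot be settled from the documents. The effect is small beside sampling error in a study that SAP Section 3.2 says is not powered for formal testing, but a larger sample would not remove it. For PFS it matters only if that comparison is judged suitable at all. This is a cheap improvement to the primary analysis and does not threaten the study.

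**What to change.** Reconcile the index-date sentence (Protocol Section 8.2.1.2, SAP Section 4.1) with the endpoint definitions (Protocol Table 1, SAP Table 2):

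1. Time OS and PFS of treated COLUMBUS patients from treatment initiation, meaning first study-drug dose. This matches the stated index date and the exposure definition.
2. Report the randomization-based analysis of all patients randomized to ENCO+BINI alongside it, as a sensitivity analysis.
3. State how never-treated COLUMBUS patients are handled in each analysis.
4. State whether Flatiron initiation is dated from an order or an administration. If from an order, acknowledge that timing COLUMBUS from first dose could leave a mismatch in the opposite direction, and read the two analyses together.
5. Report the distribution of the randomization-to-first-dose gap and the untreated count.

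Time from metastatic diagnosis to treatment initiation needs no change, since it already ends at initiation in both sources. That variable and year of initiation are listed for COLUMBUS, so the start date should be held.

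The cost is one date variable, one further model run and a few lines of text. The downsides are that COLUMBUS survival estimates will differ by days from randomization-based values, and that the first-dose analysis departs from strict intent-to-treat for any never-treated patients. The sensitivity analysis covers both.

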8.7.5. Exploratory analyses of PFS

Analyses assessing PFS will also be explored. PFS will be defined as described in Section 8.3. PFS will be summarized for all treatment groups.

Suitability of comparative analyses of PFS between treatment groups will be determined following additional data exploration to characterize number and frequency of assessments of PFS available in these settings, and discussion of comparability of the assessment of disease progression in RWD vs CTD. If analyses of PFS are deemed suitable based on these evaluations,

unadjusted and adjusted comparisons of PFS will be conducted using the methods described in Sections 8.7.2 and 8.7.4.

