2.1 STUDY DESIGN

This is a retrospective cohort study comparing OS outcomes between patients with BRAFV600-mutant metastatic melanoma initiating encorafenib plus binimetinib (ENCO+BINI) versus dabrafenib plus trametinib (DAB+TRAM) or vemurafenib plus cobimetinib (VEM+COBI). Comparisons will be adjusted for differences in baseline characteristics across treatment groups, and account for missing data on adjustment factors. PFS will also be investigated as an exploratory endpoint, subject to comparability of PFS outcome assessment between clinical trial and real-world settings.

Study population

The study population will consist of patients with BRAFV600-mutant metastatic melanoma initiating treatment with ENCO+BINI, DAB+TRAM or VEM+COBI. Data for ENCO+BINI will be pooled across COLUMBUS and Flatiron data, while data for DAB+TRAM and VEM+COBI will be from Flatiron data. The number of patients eligible for the study will be determined in accordance with the sample selection conducted per the inclusion and exclusion criteria described in Section 4.

Data source

COLUMBUS trial

COLUMBUS was a two-part, multicenter, randomized, open-label, Phase 3 clinical trial. Part 1 of the trial investigated the effectiveness and safety of three treatment regimens in patients with locally advanced unresectable or metastatic BRAFV600-mutant metastatic melanoma who were treatment naïve or whose cancer had progressed after 1L IO. In Part 1 of the trial, patients were randomized to one of three treatment arms: 1) 450mg once daily encorafenib and 45mg twice daily binimetinib (n=192), 2) 960mg twice daily vemurafenib (n=191) and 3) 300mg once daily encorafenib (n=194). Randomization was stratified by AJCC disease stage (IIIB, IIIC, IVM1a, IVM1b, or IVM1c), ECOG performance status (0, 1), and BRAFV600 mutation profile (V600E, V600K). Progression-free survival was the primary endpoint in the trial, while OS was one of the secondary endpoints. Patients were enrolled in Part 1 of the trial between 30 December 2013 through 10 April 2015.

The ENCO+BINI arm of Part 1 of the trial will be used in this study (database lock date: 15 September 2020) and combined with the ENCO+BINI cohort from Flatiron EHR identified below. Part 2 of the trial compared encorafenib 300mg once daily plus binimetinib 45mg twice daily versus encorafenib 300mg once daily alone and will not be considered.

Flatiron Health EHR

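### Exploratory PFS is censored by a different rule in COLUMBUS than in Flatiron, and the rule is tied to treatment group

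*Protocol*

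**What the plan says.** Protocol Table 1 and SAP Table 2 define PFS separately by source, in the same terms in both documents.

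- **COLUMBUS, event:** time from randomization to "the date of the first documented disease progression or death due to any cause, whichever occurred first".
- **COLUMBUS, no event:** "PFS will be censored at the date of the last adequate tumour assessment".
- **Flatiron, event:** "the time from the index date to either the date of first disease progression event or death in the absence of progression". Protocol Section 8.2.1.2 sets time zero: "The index date in each treatment group will be the date of treatment initiation".
- **Flatiron, no event:** "censored at the last date the patient could have been assessed for progression (e.g., the last clinical note date", or at the analysis cut-off, whichever is earlier.

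SAP Section 2.1 pools ENCO+BINI across the two sources, "while data for DAB+TRAM and VEM+COBI will be from Flatiron data". The same section gives the size of the COLUMBUS arm: "encorafenib and 45mg twice daily binimetinib (n=192".

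PFS is exploratory. Protocol Section 8.7.5 makes the comparison depend on a review that will "characterize number and frequency of assessments of PFS available in these settings" and will discuss whether progression is assessed comparably. Protocol Section 7 and SAP Section 2.2 add further analyses of PFS comparability between trial and real-world settings. None of these states a criterion, and none mentions the censoring date. SAP Section 3.1 and the PFS row of SAP Table 3 list the PFS comparison without repeating the condition.

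**The concern.** A clinic note need not be a disease assessment. Suppose scans stop while notes continue. Under the Flatiron rule the patient stays at risk, progression-free, until the last note. Under the COLUMBUS rule the same patient leaves the risk set at the last assessment.

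If both treatment groups drew on the two sources in similar proportions, this would largely cancel. They do not: the comparators are wholly Flatiron and ENCO+BINI is a mixture. The listed Cox covariates are baseline characteristics and cannot remove a difference in how the outcome is built. The two optional sensitivity analyses in SAP Section 7.1 concern extra covariates and the period of treatment initiation, so neither aligns the rules. A PFS hazard ratio from these definitions could therefore carry a component that comes from the rule and not from the drugs.

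**Working it through.** **No figure to reproduce.** The documents state no PFS event count, sample size, power or hazard ratio. They also give no assessment interval and no gap between last assessment and last note.

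**Mechanism.** Let C be the proportion without an event, T the mean time at risk per patient, and g the extra event-free months that the note rule adds. If no event can be recorded in the gap, the comparator event rate is divided by 1 + C·g/T, and the ENCO+BINI to comparator rate ratio rises by that factor.

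Illustration, all inputs assumed: exponential PFS with median 12 months, follow-up uniform on 3 to 36 months, ENCO+BINI all from COLUMBUS.

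- Hazard λ = ln 2 / 12 = 0.0578 per month.
- C = [exp(−3λ) − exp(−36λ)] / (33λ) = (0.841 − 0.125) / 1.906 = 0.376.
- T = (1 − C) / λ = 0.624 / 0.0578 = 10.8 months.
- Factor 1 + 0.376·g / 10.8 = 1.03, 1.10 and 1.21 for g = 1, 3 and 6 months.

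This is a rough upper guide. A Cox model uses the extra time only where it changes a risk set at an event time, deaths in the gap still count, and Flatiron patients within ENCO+BINI dilute the contrast.

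**Simulation.** True hazard ratio 1.00, one-covariate Cox model, 200 replicates per cell.

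- From the documents: 192 COLUMBUS patients censored at last assessment; comparators entirely under the Flatiron rule.
- Assumed: exponential PFS with median 8, 12 or 15 months; assessments every 2 months in both sources; follow-up uniform on 3 to 36 months; 15% of events are deaths; 10% or 30% of ENCO+BINI from Flatiron; 400 comparator patients; last note 0, 1, 3 or 6 months after last assessment.

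Hazard ratio, ENCO+BINI versus comparator (Monte Carlo standard error of the log hazard ratio 0.006 to 0.008):

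| Median PFS, Flatiron share of ENCO+BINI | Gap 0 | Gap 1 | Gap 3 | Gap 6 |
|---|---|---|---|---|
| 8 months, 10% | 1.014 | 1.000 | 1.044 | 1.127 |
| 8 months, 30% | 1.001 | 0.998 | 1.028 | 1.093 |
| 12 months, 10% | 1.004 | 1.018 | 1.043 | 1.147 |
| 12 months, 30% | 1.001 | 0.992 | 1.037 | 1.097 |
| 15 months, 10% | 1.003 | 0.991 | 1.072 | 1.148 |
| 15 months, 30% | 1.005 | 1.001 | 1.034 | 1.098 |

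With the rules aligned (gap 0) the model returns 1.00 to 1.01, as it should. A 1-month gap gives 0.99 to 1.02, a 3-month gap 1.03 to 1.07 and a 6-month gap 1.09 to 1.15. The null result at 1 month partly reflects the assumed 2-month schedule: a gap shorter than the interval leaves the risk sets at scan dates almost unchanged.

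**Variants.** These measure the gap from the end of scanning, with a mean of 1 to 3 months and median PFS 12 months. With ENCO+BINI all from COLUMBUS, one set of runs gave 1.03 to 1.16 (1.02 to 1.11 with 30% from Flatiron) and another about 1.03 to 1.20. Across all runs the range is about 0.99 to 1.20, and any material shift is against ENCO+BINI.

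**Event definitions side by side.** COLUMBUS counts the first documented progression or death from randomization; Flatiron counts the first progression or death from treatment initiation. Neither sets a minimum interval after time zero.

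**The case against.** Four points can be made for the plan.

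1. **The Flatiron rule concerns assessability.** It names the last date on which progression could have been assessed and offers the note only as an example. Protocol Section 8.4 lists physician notes among the Flatiron sources. If clinicians reliably record progression in notes without a scan, the note date is a fair assessment date and most of the simulated shift goes. This stands as a limit on size. But a note that says nothing about disease status would still extend follow-up, and the COLUMBUS rule allows no such extension.
2. **PFS is exploratory and conditional.** SAP Section 3.2 says the study is not powered for formal testing. This stands, and it limits the consequence.
3. **The suitability review might detect the problem.** An outcome-level comparison of PFS between settings could show a rule-driven shift. It could, but it has no stated criterion and would be run on the unaligned definitions.
4. **Every simulation input is assumed.** This also stands.

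A reader might infer a second difference: that Flatiron alone counts progression recorded from day 0, so that a progression which prompted the switch is charged to the new drug. The text does not support this. The COLUMBUS definition has no minimum window either, and nothing in the documents shows that Flatiron dates such progressions after index. Excluding early progressions in Flatiron alone would create an event-rule difference that does not now exist.

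**Conclusion.** The concern holds for censoring only. The two rules differ in plain text, source is tied to treatment, and no planned step aligns them.

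Under a true hazard ratio of 1.00, the rule alone gives about 0.99 to 1.20. That rests on assumed gaps of 1 to 6 months, assumed assessment intervals and follow-up, and progression going unrecorded after assessments stop. These figures show possible size; they are not estimates for this study. The shift is near nil if the gap is short or notes capture progression.

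A reader might go further and conclude that any PFS hazard ratio would be uninterpretable, or that the main result is compromised. Neither follows. The size is uncertain and may be small, and the primary OS comparison does not use this rule. The point should be settled before any PFS hazard ratio is produced.

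**What to change.** If the PFS comparison goes ahead, state one censoring rule for both sources in Protocol Table 1 and SAP Table 2.

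- **Preferred:** censor event-free Flatiron patients at the last recorded disease assessment (imaging or a clinician's assessment of progression) on or before cut-off. Report the last-note rule as a sensitivity analysis. The planned count of assessments in Protocol Section 8.7.5 already calls for this kind of data.
- **If assessment dates are not in the extract:** censor COLUMBUS at last contact or visit, so that both sources use the same kind of date. The COLUMBUS OS definition already uses last contact. This is second best, because unassessed time then enters both sources and may differ in length.
- **Progression close to time zero:** any rule should be the same in both sources and used only as a sensitivity analysis.

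The cost is a sentence or two in each table and one more derived date. Some Flatiron patients will be censored earlier, with a small loss of follow-up.
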